ViiV Healthcare has no objection to publication by Investigator of any information collected or generated by Investigator, whether or not the results are favorable to the Investigational Drug. However, to ensure against inadvertent disclosure of Confidential Information or unprotected Inventions, Investigator will provide ViiV Healthcare and/or designee an opportunity to review any proposed publication or other type of disclosure before it is submitted or otherwise disclosed.

Investigator will provide manuscripts, abstracts, or the full text of any other intended disclosure (poster presentation, invited speaker or guest lecturer presentation, etc.) to ViiV Healthcare /and/or designee at least 30 days before they are submitted for publication or otherwise disclosed. If any patent action is required to protect intellectual property rights, Investigator agrees to delay the disclosure for a period not to exceed an additional 60 days.

Investigator will, on request, remove any previously undisclosed Confidential Information (other than the Study results themselves) before disclosure.

If the Study is part of a multi-centre study, Investigator agrees that the first publication is to be a joint publication covering all centers. However, if a joint manuscript has not been submitted for publication within 12 months of completion or termination of the Study at all participating sites, Investigator is free to publish separately, subject to the other requirements of this Section.

For all publications relating to the Study, Institution will comply with recognized ethical standards concerning publications and authorship, including Section II - "Ethical Considerations in the Conduct and Reporting of Research" of the Uniform Requirements for Manuscripts Submitted to Biomedical Journals, <http://www.icmje.org/index.html#authorship>, established by the International Committee of Medical Journal Editors.

Publication of study results is also provided for in the Clinical Study Agreement between Pfizer and the Institution. In this section entitled Publications by Investigators, the defined terms shall have the meanings given to them in the Clinical Study Agreement.

Change To

Publication of study results is discussed in the Clinical Study Agreement.

Communication of Results

Where required by applicable regulatory requirements, an investigator signatory will be identified for the approval of the clinical study report. The investigator will be provided reasonable access to statistical tables, figures, and relevant reports and will have the opportunity to review the complete study results at a Sponsor site or other mutually-agreeable location.

Sponsor will also provide the investigator with the full summary of the study results. The investigator is encouraged to share the summary results with the study subjects, as appropriate.

The results summary will be posted to an internet-based study register at the time of the first regulatory approval or within 12 months of study completion or of any decision to terminate development. In addition, a manuscript will be submitted to a peer-reviewed journal for publication within 12 months of the first regulatory approval or within 12 months of study completion or of any decision to terminate development. When manuscript publication in a peer-reviewed journal is not feasible, further study information will be posted to an internet-based study register to supplement the results summary.

Publications by Investigators

ViiV Healthcare has no objection to publication by Investigator of any information collected or generated by Investigator, whether or not the results are favorable to the Investigational Drug. However, to ensure against inadvertent disclosure of Confidential Information or unprotected Inventions, Investigator will provide ViiV Healthcare and/or designee an opportunity to review any proposed publication or other type of disclosure before it is submitted or otherwise disclosed.

Investigator will provide manuscripts, abstracts, or the full text of any other intended disclosure (poster presentation, invited speaker or guest lecturer presentation, etc.) to ViiV Healthcare /and/or designee at least 30 days before they are submitted for publication or otherwise disclosed. If any patent action is required to protect intellectual property rights, Investigator agrees to delay the disclosure for a period not to exceed an additional 60 days.

Investigator will, on request, remove any previously undisclosed Confidential Information (other than the Study results themselves) before disclosure.

If the Study is part of a multi-centre study, Investigator agrees that the first publication is to be a joint publication covering all centers. However, if a joint manuscript has not been submitted for publication within 12 months of completion or termination of the Study at all participating sites, Investigator is free to publish separately, subject to the other requirements of this Section.

For all publications relating to the Study, Institution will comply with recognized ethical standards concerning publications and authorship, including Section II - "Ethical Considerations in the Conduct and Reporting of Research" of the Uniform Requirements for

Manuscripts Submitted to Biomedical Journals, <http://www.icmje.org/index.html#authorship>, established by the International Committee of Medical Journal Editors.

Publication of study results is also provided for in the Clinical Study Agreement between Pfizer and the Institution. In this section entitled Publications by Investigators, the defined terms shall have the meanings given to them in the Clinical Study Agreement.

22. Section 15.1; Scientific Steering Committee

Change From

Last sentence

... In the event of recommendations for a significant change by the SSC, ~~Pfizer~~ **the Sponsor** will notify regulatory agencies where necessary, as per legal or regulatory requirements.

Change To

... In the event of recommendations for a significant change by the SSC, the Sponsor will notify regulatory agencies where necessary, as per legal or regulatory requirements

## 1. AMENDMENTS FROM PREVIOUS VERSION(S)

This amendment outlines the change implemented in protocol amendment #3 of Nov 29 2010, from enrolling 2000 maraviroc-exposed and 1000 maraviroc-unexposed patients to enrolling 1500 patients in each arm.

## 2. INTRODUCTION

NOTE: *Italicized* text within this document has been taken verbatim from the Protocol.

*Maraviroc, in combination with other antiretroviral medicinal products, is indicated for treatment-experienced adult patients infected with only CCR5-tropic HIV-1 detectable. There is limited information about the safety of long-term treatment with maraviroc. No signal for increased risk of hepatotoxicity, malignancy or infection has been observed in the clinical development program for maraviroc through 48 weeks of therapy. However, the concern that hepatotoxicity is a CCR5 antagonist class effect and the theoretical risk of altered immune function leading to altered rates or severity of malignancy or infections, including opportunistic infections (OI) remain to be fully addressed. Given the imbalance in the incidence of myocardial ischemic events in the ongoing clinical trials of maraviroc, data on long-term follow-up for MI and myocardial ischemia incidence in patients receiving maraviroc along with HAART would more fully characterize this potential safety risk. As most of these patients receive lipid-lowering agents that may be associated with a heightened risk of rhabdomyolysis, it is of interest to examine the incidence of this event. All-cause mortality will also provide information regarding any possible long term implications of treatment with maraviroc.*

*The objective of this international, multicenter, prospective observational comparative study is to monitor the safety of long term use of maraviroc in a larger and more diverse patient population than that in which the Phase 2b/3 clinical trials were conducted. By providing additional data regarding long-term use of maraviroc, this study will help further characterize the safety profile of the drug.*

### 2.1. Study Design

*This is an international, multicenter, open-label, comparative, prospective observational epidemiologic study.*

*The study will enroll 1500 HIV-1 infected, treatment-experienced adult patients who have been prescribed maraviroc along with an optimized background antiretroviral therapy (OBT) regimen in usual clinical practice following the approved local label of maraviroc.*

*The internal comparator group will consist of 1500 HIV-1 infected, treatment-experienced adult patients receiving OBT who received an HIV-1 tropism assay as a screening test for eligibility to receive maraviroc in usual clinical practice but were not prescribed maraviroc. This group may include patients infected with dual/mixed tropic or CXCR4 tropic HIV-1 as well as patients infected with CCR5 tropic HIV-1.*

The subject enrollment scheme is presented in [Appendix 2](#).

The study will be conducted at approximately 300 sites in multiple countries. Participating countries were chosen on the basis of extensive feasibility assessments and include: Belgium, Brazil, Canada, France, Germany, Greece, Italy, Portugal, Spain, United Kingdom, and United States. If required, additional countries may be added and some countries in this initially proposed list may be dropped. Countries will participate only after maraviroc is approved by Health Authorities in that country and is commercially available. Enrollment will be competitive and recruitment of subjects will terminate after the global target sample size is achieved. The expected numbers of subjects in the participating countries are provided in Table 1. Initial enrollment goals set for each country will be redistributed if necessary. Barring unforeseen circumstances (eg, significant delays in marketing authorization approval in countries, marked delays in regulatory approvals of the study protocol in countries, etc.), enrollment is expected to commence in 1Q2008 and is anticipated to continue for approximately 30 months. The enrollment status will be continuously monitored by the Sponsor and the external Scientific Steering Committee overseeing the study. If required, the enrollment period will be extended to enroll the necessary sample size.

**Table 1. Enrollment targets by country**

Countries	Expected number of study subjects	Projected launch date for commercial Maraviroc
Belgium	80	March 2008
France	200	April 2008
Germany	223	October 2007
Greece	40	March 2008
Italy	140	March 2008
Portugal	35	April 2008
Spain	250	May 2008
UK	161	November 2007
USA	1700	August 2007
Canada	80	October 2007
Brazil	91	May 2008

There will be no protocol-mandated patient visits or laboratory tests in this study. Therefore, visits are scheduled following the local guidelines and/or clinical practices. However, most guidelines recommend follow-up visits at weeks 2-4 after initiating a new therapy to assess initial viral response and address issues affecting adherence, then again at weeks 8 and 12, and then every 12 weeks thereafter. All subjects will be observed for five years.

## 2.2. Study Objectives

1. To estimate the incidence rates of (a) Centers for Disease Control and Prevention category C AIDS-defining opportunistic infections (OI), (b) Viral encephalitis,

*(c) Liver failure, and (d) Rhabdomyolysis, in treatment-experienced HIV-1 patients receiving maraviroc during time of use and for up to six months following discontinuation of maraviroc treatment, up to a total of five years since entry into the study.*

2. *To estimate the incidence rates of (a) myocardial infarction (MI) or ischemia, (b) all malignancies, (c) all cause mortality, and (d) liver related deaths in treatment-experienced HIV-1 infected patients receiving maraviroc for up to five years after entry into the study regardless of the actual duration of maraviroc use.*
3. *To compare the rates of the study endpoints in patients receiving maraviroc to those observed in an internal comparator group of treatment-experienced, HIV-1 infected patients not receiving maraviroc.*
4. *To compare the observed rates of the study endpoints in patients receiving maraviroc in this study to those observed in HIV-1 infected patients not receiving maraviroc in an appropriate external comparator cohort (eg, EuroSIDA).*

### **3. INTERIM ANALYSES, FINAL ANALYSES AND UNBLINDING**

Periodic review of the study progress and assessment of collected data will be conducted by the Scientific Steering Committee (SSC) once in every six months. The data to be reviewed by the Steering Committee will be outlined in a separate analysis plan. In addition, yearly progress reports will be provided to the regulatory agencies throughout the duration of the study. The analyses as outlined in Section 8.2 will be adopted for reporting these results. There are no formal stopping rules for the study; however, the SSC may recommend stopping the study for safety issues at any time.

Full final analysis will follow the official database release. Since this is an open label study, no formal un-blinding of the randomization is needed.

### **4. HYPOTHESES AND DECISION RULES**

#### **4.1. Statistical Hypotheses**

None

#### **4.2. Statistical Decision Rules**

##### **4.2.1. Sample Size**

*The sample size for the study was determined based on an extensive feasibility assessment in 28 countries, input from Pfizer country offices, and in consultation with the regulators. This number was estimated to be 3,000 subjects (1,500 patients receiving maraviroc and 1,500 patients not receiving maraviroc) to allow calculations of reliable and precise risk estimates.*

*Malignancies, myocardial ischemia or infarction and deaths (liver-related and all cause) occurring at any time during the 5-year follow-up period will be adjudicated and analyzed as study endpoints. Assuming up to 10% annual loss to follow-up, the 1,500 patients each receiving maraviroc or the anchor drug will contribute 5,836 person-years of observation for these study endpoints over a 5-year period (See Scenario 1 in Appendix 3 for details) in each treatment arm. It is assumed that the expected incidence rates are 12.7 per 1000 person-years for malignancies, (Beral, V. et al, 2000) 5 per 1,000 person-years for myocardial infarction, (Friis-Moller, N, et al, 2003) 2.35 per 1,000 person-years for liver-related deaths, (Weber, R, et al 2006) and 16 per 1,000 person-years for all cause mortality (Weber, R, et al 2006) in the internal comparator group of patients not receiving maraviroc.*

*CDC category C AIDS-defining opportunistic infections, viral encephalitis, rhabdomyolysis and liver failure will be adjudicated and analyzed as study endpoints if they occur during the use of maraviroc or the anchor drug in the OBT arm or within 6 months following maraviroc or anchor drug discontinuation. Accounting for the expected rates of drug discontinuation in the two treatment arms over time and a 10% annual loss to follow-up, each study arm will accrue 2,875 person-years of observation for these study endpoints (See Scenario 2 in Appendix 3 for details). It is assumed that the expected incidence rates are 3.5 per 1,000 person-years for liver failure, (Friis-Moller, N., Kirk O, Reiss P, 2003) and 160 per 1,000 person-years for AIDS-defining opportunistic infections (Kaplan, J.E., et al., 2000) in the internal comparator group of patients not receiving maraviroc.*

Based on these assumptions of equal person years of contribution in the maraviroc exposed and unexposed groups, using a two-tailed test with  $\alpha=0.05$ , and a power of 80%, the minimum detectable relative rates for various study end points are reported in Table 2. (McMahon, A.D. and T.M. MacDonald, 1997).

**Table 2. Minimum detectable relative rates using a two sided test,  $\alpha =0.05$ , and a power of 80%**

End Point	Expected number of events in the unexposed internal comparator group	Detectable Relative rates
Malignancies	74	1.572
AIDS-defining opportunistic infections	460	1.1955
Myocardial infarction	20	2.136
Liver failure	10	2.760
Liver-related deaths	14	2.410
All cause mortality	93	1.464

*For example, results from Table 2 suggest that the study has 80% power to detect a relative risk of  $\geq 1.527$  for malignancies and  $\geq 1.196$  for AIDS-defining opportunistic infections, respectively for the patients receiving maraviroc. Similar conclusions can be drawn for other end points as well.*

#### 4.2.2. Estimation of follow up time

Patients enrolled in the maraviroc-exposed group: all follow up time accrued in the study will be contributed to the “maraviroc-exposed” group regardless of the actual duration of maraviroc use.

Patients enrolled in the maraviroc-unexposed group: all follow up time accrued in the study will be contributed to the “maraviroc-unexposed” group regardless of the actual duration of the use of the anchor drug in the OBT. If a patient starts maraviroc during the study, the follow up time accrued before starting maraviroc will be applied to the “maraviroc-unexposed” group and the follow up time accrued after starting maraviroc will be applied to the “maraviroc-exposed” group.

For the maraviroc unexposed group, the anchor drug in the OBT regimen is identified according to the following hierarchy:

- ▶ Raltegravir or other integrase inhibitor
  - ▶ Enfuvirtide or other fusion inhibitor
    - ▶ Etravirine or other second generation NNRTI
      - ▶ Darunavir or other protease inhibitor

The following are the currently commercially available drugs in each class at the time of the finalization of the SAP:

Protease Inhibitors (PI):

- ▶ tipranavir, indinavir, saquinavir, lopinavir, fosamprenavir, ritonavir, darunavir, atazanavir, nelfinavir

Nucleoside/Nucleotide Reverse Transcriptase Inhibitors (NRTI):

- ▶ emtricitabine, lamivudine, zalcitabine, zidovudine, didanosine, tenofovir disoproxil fumarate, stavudine, abacavir

Non-Nucleoside Reverse Transcriptase Inhibitors (NNRTI):

- ▶ delavirdine, efavirenz, nevirapine, etravirine

Fusion Inhibitors:

- ▶ enfuvirtide

Entry Inhibitors:

- ▶ maraviroc

Integrase Inhibitors:

- ▶ raltegravir

Patients starting CCR5 inhibitors other than maraviroc: In both groups, follow up will be terminated if a patient starts using any CCR5 inhibitor (either experimental or commercially available) other than maraviroc.

Patients switching to a non-participating physician: If the patient does not withdraw consent, follow up will continue. In these cases, only the mortality endpoints will be collected via direct patient contact by a CRO.

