2. STUDY OBJECTIVES AND ENDPOINTS

2.1. Objectives

1. To estimate the incidence rates of: (a) Centers for Disease Control and Prevention category C AIDS-defining opportunistic infections (OI), (b) viral encephalitis, (c) liver failure, and (d) rhabdomyolysis in treatment-experienced HIV-1 infected patients receiving maraviroc during time of use and for up to six months following discontinuation of maraviroc treatment, up to a total of five years since entry into the study.
2. To estimate the incidence rates of (a) myocardial infarction (MI) or ischemia, (b) all malignancies, (c) all cause mortality, and (d) liver related deaths in treatment-experienced HIV-1 infected patients receiving maraviroc for up to five years after entry into the study regardless of the actual duration of maraviroc use.
3. To compare the rates of the study endpoints in patients receiving maraviroc to those observed in an internal comparator group of treatment-experienced, HIV-1 infected patients not receiving maraviroc.
4. To compare the observed rates of the study endpoints in patients receiving maraviroc in this study to those observed in HIV-1 infected patients not receiving maraviroc in an appropriate external comparator cohort (eg, EuroSIDA).

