6.5. Follow-up of patients switched to non-participating physicians

If for any reason (eg, relocation, insurance change) a patient switches to a physician who is not participating in the study, the patient will be discontinued from the study. The enrolling physician will complete a follow up questionnaire with the last available clinical data and the subject summary module of the questionnaire. If the patient does not withdraw consent to participate in the study, an attempt will be made to ascertain the vital status of the patient as mentioned in Section 6.4 for patients lost to follow up.

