Study endpoints that are closely temporally related to drug exposures ie, CDC category C opportunistic infections, viral encephalitis, rhabdomyolysis and liver failure will cease to be adjudicated as study endpoints after six months following discontinuation of maraviroc. For patients in the maraviroc unexposed comparator group, adjudication of these events will cease after six months following discontinuation of the anchor drug in their OBT as identified at baseline (Section 7.2). If these events are diagnosed after this cut-off period, they will be considered as any other adverse event and reported per the Adverse Event Reporting guidelines described in Section 8, which requires the collection and reporting of all serious adverse events (SAE) and all adverse reactions. Occurrence of myocardial infarction or ischemia, malignancies, and death (all-cause and liver-related) will be reported and adjudicated as study endpoints for up to five years following enrollment.

The follow-up duration for malignancies may be extended beyond five years if, based on emerging safety data, the Scientific Steering Committee (SSC) overseeing the study recommends a longer period of observation. Due to the potentially prolonged time required for a malignancy to become clinically apparent, a search of national and state cancer and death registries will be performed to look for all episodes of malignancy within 10 years of study entry for all subjects in countries where such registries are available, are accessible for research purposes and where such search is allowed by local law. Active study participation of subjects will be for only 5 years, but informed consent will be obtained at enrollment allowing for passive subject follow-up beyond the 5 years of active participation through this additional search of cancer and vital status registries. This search will be conducted by a designated CRO or professional search firm using appropriate national identifiers collected at enrollment. The investigators will not have to do the search.

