## 6. ENDPOINTS AND COVARIATES

### 6.1. Study Endpoint(s)

The study endpoints are:

1. Centers for Disease Control and Prevention Category C AIDS-defining opportunistic infections will be considered as study end points up to 6 months post-discontinuation of maraviroc or the anchor drug in the OBT ([Appendix 1](#)). After 6-months, these clinical events will be handled as AE.
2. All malignancies up to five years of follow-up will be considered as study endpoints.
3. Liver failure will be considered as study endpoints up to 6 months post-discontinuation of maraviroc or the anchor drug in the OBT. After 6-months, these clinical events will be handled as AE.

4. Myocardial infarction or ischemia up to five years of follow-up will be considered as study endpoints.
5. Death from liver-related cause up to five years of follow-up will be considered as study endpoints.
6. Death from any cause up to five years of follow-up will be considered as study endpoints.

In addition, the following will be considered as study end points up to 6 months post-discontinuation of maraviroc or the anchor drug in the OBT:

- viral encephalitis
- rhabdomyolysis

After 6-months, these clinical events will be handled as AE.

The operational diagnostic criteria of each endpoint are described in the endpoint adjudication manual for this study.

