#### **Expected person-time of observation in:**

These events will be adjudicated and analyzed as study endpoints if they occur during use of maraviroc or the anchor drug in the OBT, or within 6 months following their discontinuation

- Based on clinical experience, it is assumed that the rate of drug discontinuation will be higher in the earlier part of the study and will gradually decrease over time. To obtain a conservative estimate, it is assumed based on the observations from the 48-week clinical development program of maraviroc that the rate of discontinuation will be approximately 30% during the first 6 months of therapy, 25% between the 7th and 12th month, 20% between the 13th and 18th months and 15% in each 6 month period thereafter. For the purpose of this calculation it is assumed that on average discontinuation occurs at the midpoint of each 6-month period.

- It is assumed that 5% of the patients (either continuing maraviroc or during the 6 months post discontinuation follow-up) will be lost every 6 months and on average these losses will occur at the midpoint of the 6-month period.
- Patients lost to follow-up during any 6-month period (either on or off maraviroc) will contribute only 3 months of follow-up time during that period. Patients who are being actively followed up at the end of each 6-month period will contribute 6 months of follow-up time.

Based on the above assumptions, both these groups will accrue 2875 person-years of follow-up during the study for the assessment of AIDS-defining OI, viral encephalitis, rhabdomyolysis and liver failure.

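### The SAP counts all follow-up time for every endpoint, although four endpoints stop counting 6 months after drug stop and patients who change physician are followed for mortality only

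*SAP*

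**What the plan says.** **Person-time.** SAP 4.2.2 is the only analysis rule that allocates follow-up. In the maraviroc arm, "all follow up time accrued in the study will be contributed to the “maraviroc-exposed” group regardless of the actual duration of maraviroc use". In the comparator arm, time goes to the unexposed "group regardless of the actual duration of the use of the anchor drug in the OBT", except that time after a patient starts maraviroc moves to the exposed group. No endpoint is treated differently.

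**Which events count.** SAP 6.1 limits four endpoints by time since drug stop, for example: "Liver failure will be considered as study endpoints up to 6 months post-discontinuation of maraviroc or the anchor drug in the OBT". OI, viral encephalitis and rhabdomyolysis have the same limit, and later cases are handled as adverse events. Protocol 7.4 agrees: these events "will cease to be adjudicated as study endpoints after six months following discontinuation of maraviroc", with the matching anchor-drug cut-off for comparators. Objective 1 (Protocol 2.1) asks for their rates in patients "receiving maraviroc during time of use and for up to six months following discontinuation of maraviroc treatment".

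**Planned person-time.** SAP Appendix 3, Scenario 2, states that "both these groups will accrue 2875 person-years of follow-up during the study for the assessment of AIDS-defining OI" and the other three time-limited endpoints. Scenario 1 gives 5,835 per arm for malignancy, myocardial events and deaths.

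**Change of physician.** SAP 4.2.2: "If the patient does not withdraw consent, follow up will continue. In these cases, only the mortality endpoints will be collected". Protocol 6.5 differs: if "a patient switches to a physician who is not participating in the study, the patient will be discontinued from the study", and a later vital-status search is all that remains.

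**The concern.** For the four time-limited endpoints, a patient more than 6 months past drug stop cannot contribute an event but still contributes person-time. The incidence density is then too low in each arm. This matters most for Objective 1, which is absolute estimation, and for Objective 4, where the rates are set against an external cohort and nothing cancels.

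The internal rate ratio is affected when the arms stop their drugs at different speeds. The arm that stops sooner collects more time in which no event can count, and so looks safer. In a post-approval safety study, faster maraviroc discontinuation could hide an excess risk. The propensity-score adjustment in SAP 8.2 addresses baseline covariates and cannot correct this. Under SAP 3, the yearly reports to regulators use the Section 8.2 analyses, so the error would recur each year.

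Patients who change physician raise the same problem for myocardial infarction or ischemia and malignancy, because their later time carries no possibility of a recorded event.

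**Working it through.** **Inputs.** 1,500 patients per arm. Scenario 1: 10% lost per year, at mid-year. Scenario 2: drug discontinuation of 30%, 25% and 20% in the first three 6-month periods and 15% in each later one, at mid-period, with 5% lost per 6 months (Appendix 3 of both documents). Comparator rates of 160 (OI) and 3.5 (liver failure) per 1,000 person-years (SAP 4.2.1).

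**Step 1: reproduce Scenario 1.** Each year gives 0.95 × the number at its start: 0.95 × 1,500 × (1 + 0.9 + 0.9² + 0.9³ + 0.9⁴) = 5,835.5. The plan states 5,835 in Appendix 3 and 5,836 in the text.

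**Step 2: reproduce Scenario 2.** Apply loss first. Patients who continue or discontinue in a period give 0.5 year and those lost give 0.25. Those who discontinued in the previous period give 0.25 year more, the rest of their 6 months.
- Period 1: 75 lost, 427.5 discontinue, 997.5 continue. Person-years: 0.5 × 1,425 + 0.25 × 75 = 731.2.
- Period 2: 49.9 lost, 236.9 discontinue, 710.7 continue. Person-years: 486.3 + 0.25 × 427.5 = 593.2.
- Carried through ten periods, the total is 2,898.

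Other orderings of loss and discontinuation give 2,797 to 2,927. The stated 2,875 lies inside that range.

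**Step 3: reproduce the expected events.** OI: 0.160 × 2,875 = 460. Liver failure: 0.0035 × 2,875 = 10.06. Both match Table 2, so the plan's event counts rest on the limited window.

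**Step 4: apply SAP 4.2.2 as written.** The events stay the same and the denominator becomes 5,835.

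| Endpoint | Events | Per 1,000 over 2,875 | Per 1,000 over 5,835 |
|---|---|---|---|
| OI | 460 | 160 | 78.8 |
| Liver failure | 10.06 | 3.5 | 1.72 |

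The factor is 2,875 / 5,835 = 0.493. Per arm, 5,835 − 2,875 = 2,960 person-years are counted in which these events cannot be.

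**Step 5: rate ratio when the true ratio is 1.0.** With equal full denominators, the apparent ratio is maraviroc window time divided by comparator window time. Maraviroc stays at the planned discontinuation (2,898). The comparator multipliers are assumptions; the documents give no separate anchor-drug rates.

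| Comparator discontinuation | Window person-years | Apparent ratio |
|---|---|---|
| 0.5 × planned | 4,055 | 2,898 / 4,055 = 0.71 |
| 0.75 × planned | 3,411 | 2,898 / 3,411 = 0.85 |
| As planned | 2,898 | 1.00 |
| 1.25 × planned | 2,488 | 2,898 / 2,488 = 1.16 |

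Applying loss and discontinuation simultaneously gives 2,797 / 3,975 = 0.70, 2,797 / 3,316 = 0.84 and 2,797 / 2,387 = 1.17. For comparison, Table 2 gives the detectable OI ratio as 1.1955.

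**Step 6: patients who change physician.** Assume that 1, 3 or 5 of the 10 percentage points of annual loss are such patients and that all are kept to year 5. If 1% of each year's starters switch at mid-year, the added time is 0.01 × (1,500 × 4.5 + 1,350 × 3.5 + 1,215 × 2.5 + 1,093.5 × 1.5 + 984.15 × 0.5) = 166 person-years. At 3% it is 499 and at 5% it is 832. Against 5,835, non-mortality denominators grow by 2.9%, 8.6% and 14.3%. If switchers are instead subject to the remaining annual loss, the 1% and 5% cases give denominators of 5,984 and 6,617, and rates understated by 2.5% and 12%.

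**The case against.** The strongest reply is that SAP 4.2.2 only says which arm receives a patient's time, chiefly to settle crossover, and was never meant to define denominators. Its phrase about actual duration of use also appears in Objective 2, which covers myocardial events, malignancy and deaths; for those endpoints the rule is right apart from patients who change physician. Objective 1, SAP 4.2.1 and Scenario 2 all show that window-limited time was intended for the other four. That is good evidence of intent. But the latter two are sample-size text, and SAP 8.2 asks for incidence densities, rate ratios and Cox models with no censoring rule by endpoint. A programmer following the SAP literally would use all follow-up.

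Several limits do stand:
- The one-half figure depends on the planned discontinuation rates, which the plan itself calls conservative. If both arms stopped at 0.75 or 0.5 times those rates, the four rates would be about 58% (3,411 / 5,835) or 69% (4,055 / 5,835) of their true values.
- The plan assumes equal discontinuation in both arms, and then the dilution cancels in the ratio. The multipliers in Step 5 only illustrate what happens otherwise.
- The 14.3% for patients who change physician is an upper figure: it assumes half of all losses are such patients and that none later dies or is lost. The problem largely disappears if Protocol 6.5 governs, but the SAP currently says otherwise.
- Mortality endpoints are not diluted.

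**Conclusion.** The concern holds and should be corrected before analysis. The mismatch between the event window and the person-time needs no assumption: it follows from SAP 4.2.2 set beside SAP 6.1, Protocol 7.4 and Objective 1. Under the plan's own discontinuation and loss rates, it reduces the four time-limited incidence rates to 0.493 of their intended value. Bias in the rate ratio is conditional on the arms differing in discontinuation or switching. Across the assumed multipliers of 0.5 to 1.25 for the comparator, a null ratio appears as 0.71 to 1.16, a distortion comparable to the OI effect the study is sized to detect. The dilution from patients who change physician is secondary: 2.9% to 14.3% more person-time for non-mortality endpoints if 1 to 5 points of the annual loss are such patients, and it rests on SAP text that conflicts with the current protocol.

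**What to change.** Make person-time endpoint-specific in SAP 4.2.2 and refer to it from SAP 8.2, so that it governs the rates, the Poisson models and the survival analyses alike.

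- **OI, viral encephalitis, liver failure, rhabdomyolysis:** end person-time at the earliest of the event (for first-event analyses), 6 months after maraviroc or anchor-drug stop, last clinical encounter, death, other end of follow-up, or 5 years.
- **Myocardial infarction or ischemia, malignancy, deaths:** keep the all-follow-up rule.
- **Move to a non-participating physician:** censor all adjudicated endpoints at the last encounter with the enrolling physician, and use later vital status only in the supplementary mortality analysis. This agrees with discontinuation under Protocol 6.5, but that section gives no censoring date, so the SAP must state one.
- **Cases to spell out:** comparator patients who start maraviroc within 6 months of stopping the anchor drug (events should follow the same split as their time), patients who stop and restart a drug, and comparator regimens with no drug from the listed anchor classes.

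The cost is SAP wording and programming; no new visits or tests are needed. Protocol 6.3 records the maraviroc stop date. The anchor-drug stop date is not named as explicitly, but Protocol 7.3 collects medication use and the Protocol 7.4 cut-off already requires it, so confirm that the follow-up questionnaire captures it.
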